##### Secondary objective

The secondary objective of this study is to evaluate safety of a single intracavernous injection of *h*Maxi-K, either 8,000 or 16,000 µg, compared to placebo.

##### Study Endpoints

The primary outcome measures that will be considered to evaluate change in erectile status from baseline following administration of *h*Maxi-K are

- o Erectile Function (EF) domain of the International Index of Erectile Function (IIEF)

**ION04ED**

- Sexual Encounter Profile (SEP)-Questions 2 and 3

The safety and tolerability of the study drug will be evaluated by analysis of

- Adverse events
- Clinical laboratory tests
- Electrocardiogram
- Physical examinations including vital signs

## 5. Analysis Sets

- **Randomized population:** This will include all the subjects who have been randomized to either of the treatment groups.
- **ITT population:** This will include all the subjects who have been randomized to either of the treatment groups and who have received at least one dose of study treatment.
- **Modified ITT population (Mod-ITT population):** This population will include all subjects in the ITT population who have at least one post dose efficacy assessment.
- **Per Protocol Population (PP Population):** This will include all subjects in the ITT population who report no protocol violations.
- **Safety Population:** This will include all subjects who were randomized to either of the treatment groups and who have received at least one dose of study treatment.

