9.0 Adverse Events Definitions and Monitoring

9.1 Adverse Event

An adverse event is any unfavorable and unintended diagnosis, symptom, sign (including an abnormal laboratory finding), syndrome or disease which either occurs during the study, having been absent at baseline, or, if present at baseline, appears to worsen.

A treatment emergent adverse event (TEAE) will be considered an event that is temporally associated with the use of the study drug, whether or not considered related to the study drug.

Examples of AEs are as follows:

- Changes in the general condition of the participant
- Subjective symptoms offered by or elicited from the participant
- Objective signs observed by the Investigator or other study personnel
- All concurrent diseases that occur after the start of the study, including any change in severity or frequency of preexisting disease
- All clinically relevant abnormalities in laboratory values or clinically relevant physical findings that occur during the study.

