9.5 Monitoring of Adverse events

The investigator(s) will monitor their participants for the occurrence of adverse events during the course of the study and record all observed adverse events in the case report form.

Adverse Events regardless of seriousness or relationship to study drug, including those

occurring during the Screening period (where applicable), are to be recorded in the CRF. Whenever possible, symptoms should be grouped as a single syndrome or diagnosis. The Investigator should specify the date of onset, maximal intensity, corrective therapy given, outcome, and his/her opinion as to whether there is a reasonable possibility that the Adverse Event was caused by the study drug.

Any adverse events that meet the 4 criteria under Stopping Rules (Section 5.2.1) must be communicated to the sponsor (or designee) within 24 hours of first knowledge of such event

The investigator must provide the sponsor appropriate information concerning any findings suggesting significant hazards, contraindications, side effects or precautions pertinent to the safety of the study drug. The investigator will instruct participants prior to administration of study drug to report any physical changes or new symptoms that they notice during the course of the study. The investigator must report all serious adverse events (defined above) within 24 hours of their onset to Ion Channel Innovations, LLC.:

[REDACTED] M.D.

[name]

[name]

[contact]

[contact]

In case of prolongation of $QT_cF \geq 500$ ms, or an increase in $QT_cF \geq 60$ ms from baseline, a blood sample should be drawn for measurement of serum potassium, calcium, magnesium, and *hSlo* cDNA.

A cardiologist should be consulted, and the participant should continue to have his ECG monitored until the ECG abnormality resolves or becomes stable.

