10.0 Assessment of Endpoints

10.1 Safety

Safety and tolerability of the study drug will be evaluated by analysis of adverse experiences, clinical laboratory tests, electrocardiogram, and physical examinations. It will be conducted in all subjects who received treatment or there was an attempt to provide treatment.

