12.0 Regulatory Standards

12.1 Electronic case report forms

An electronic case report form (E-CRF) will be completed for every participant who signed a written Informed Consent form and receives study drug. Any correction of data recorded onto the E-CRF will be entered in to the E-CRF which will create an electronic audit trail of the corrections and electronic signature of the study personnel who made the changes.

The principal investigator must sign and date the certification form of each case report upon completion. This signature will indicate that thorough inspection of the data has been made and will thereby certify the contents of the electronic case report forms.

The investigator or institution will retain all original source documentation (e.g., laboratory results, treatment records, audit queries, etc.) unless specified otherwise by the protocol. The results as they become available will be entered on the appropriate electronic case report forms.

Electronic case report forms will be reviewed at the study site by a clinical monitor who will make a decision as to their acceptability in regard to completeness and accuracy of the data. Audit queries will be generated for omissions, corrections, and clarifications.

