## 6. Definition

- **Age:** The age will be calculated as the exact number of days between the date of birth and date of informed consent converted to years (i.e. difference in days/365.25). Age is the integer part of this value.
- **Baseline:** The time point at which randomization is performed will be the baseline time point. The last instance of data collected before administration of treatment will be considered as the baseline information for the respective parameter. If a patient has repeated assessments prior to the start of double-blind study drug, then the results from the final assessment made prior to the start of double-blind study drug will be used as baseline.
- **Body Mass Index (BMI):** BMI is obtained by dividing the weight (kg) by the square of height (m) i.e. weight (kg)/ height (m).
- **Change between baseline and post dose visits** for the parameters will be considered as the difference between the post baseline value and the baseline value (post baseline value – baseline value). This will be applicable to laboratory data and safety parameters.
- **Prior/ Concomitant Medication/Therapy:** All medications/therapies with end date prior to the date of treatment will be considered as prior medications. Concomitant medication will be defined as any medication taken between the day of dosing with study drug and the end of the 6 month study follow-up period (or final visit). Any medications started after the final visit will not be considered concomitant medications.
- **Treatment Emergent Adverse Events (TEAEs):** A treatment emergent adverse event (TEAE) will be considered as an event that is temporally associated with the use of the study drug, whether or not considered related to the study drug. All adverse events with start date on or after the date of treatment will be considered as TEAEs.

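### The SAP safety set leaves out men in whom injection was attempted but not given, and its date-only rule for treatment-emergent events has no clause for worsening

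*SAP*

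**What the plan says.** **Who is in the safety analysis.** Protocol 10.1 states of the safety evaluation: "It will be conducted in all subjects who received treatment or there was an attempt to provide treatment". SAP section 5 defines its safety population differently: "This will include all subjects who were randomized to either of the treatment groups and who have received at least one dose of study treatment". SAP section 9.4 uses that population as the denominator for adverse event percentages.

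**Whose data are collected.** Protocol 12.1 says: "An electronic case report form (E-CRF) will be completed for every participant who signed a written Informed Consent form and receives study drug". Protocol 9.5 is broader. It covers adverse events whatever their seriousness or relationship to study drug, and says that those "occurring during the Screening period (where applicable), are to be recorded in the CRF".

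**What counts as an event.** Protocol 9.1 counts an event "having been absent at baseline, or, if present at baseline, appears to worsen", and lists a change in severity or frequency of pre-existing disease among its examples. For each event, Protocol 9.5 asks for a single onset and a peak: "The Investigator should specify the date of onset, maximal intensity, corrective therapy given, outcome".

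**What counts as treatment-emergent.** SAP section 6 repeats the protocol's general idea of a temporal link with study drug and then gives a working rule: "All adverse events with start date on or after the date of treatment will be considered as TEAEs". SAP 9.4 reserves the detailed tables for events that meet this definition.

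**The concern.** Safety is the primary objective in Protocol 2.0. Two groups of events may fail to reach the main safety tables.

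The first group is events in men for whom injection was attempted but no drug was given. Protocol 10.1 includes these men by name and the SAP set does not. If no eCRF is completed for such a man, the listings may lack his event too.

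The second group is adverse events that begin after screening but before injection and become worse afterwards. With one onset date and one maximal intensity, such an event keeps its pre-dose date. The date rule then keeps it out of the tables by severity, relationship and dose-limiting toxicity. The same rule has the opposite effect on the day of injection, because it works on dates and cannot separate an event in the morning from a dose in the afternoon.

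With planned arms of 11, 11 and 13, a single misplaced man visibly changes an arm's incidence.

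**Working it through.** The documents give no figure to reproduce, so the check is a comparison of text followed by simple proportions.

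**Step 1. Attempted injections.** Take a randomized man who reacts during the procedure before any drug enters.
- Protocol 10.1: in the safety evaluation, because treatment was attempted.
- SAP section 5: out, because he received no dose. The SAP's ITT set uses the same criterion and does not include him either.
- Protocol 12.1: not among those for whom eCRF completion is required. Protocol 9.5: his event is to be recorded in the CRF. The two sections disagree.
- SAP section 6: he has no treatment date, so the date rule cannot classify his event even if he were added to the safety set.

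**Step 2. Partial injections.** Protocol 5.2 foresees drug being only partly administered because of an adverse event during injection. SAP section 5 does not say whether that meets its one-dose requirement.

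**Step 3. Size for one attempted-but-undosed man with an event.** Let n be the planned arm size (11 or 13, Protocol synopsis) and k the number of other men in the arm with an event. He leaves both numerator and denominator under the SAP, so:
- SAP set: k/(n − 1)
- Protocol set: (k + 1)/n

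| n | k | SAP set | Protocol set |
|---|---|---|---|
| 11 | 0 | 0/10 = 0% | 1/11 = 9.1% |
| 11 | 1 | 1/10 = 10.0% | 2/11 = 18.2% |
| 11 | 2 | 2/10 = 20.0% | 3/11 = 27.3% |
| 13 | 0 | 0/12 = 0% | 1/13 = 7.7% |
| 13 | 1 | 1/12 = 8.3% | 2/13 = 15.4% |
| 13 | 2 | 2/12 = 16.7% | 3/13 = 23.1% |

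**Step 4. Worsening after a pre-dose onset.** Protocol 7.2 collects adverse events since screening at Visit 2, and Appendix B places screening at week −2, so the window is about two weeks per man. An event starting in that window has a start date before treatment and does not meet the SAP's working rule, even if its grade rises after injection. It is counted only if the site enters the worsening as a new record with its own date, and neither document asks for that. The man was dosed, so the denominator does not change. One such event lowers the arm's treatment-emergent incidence by 1/11 = 9.1 points or 1/13 = 7.7 points, provided he has no other event of the kind being tabulated.

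**Step 5. Events on the dosing day.** An event that starts on the date of treatment but before injection meets the date rule. It raises incidence by the same 9.1 or 7.7 points, on the same proviso. Steps 4 and 5 pull in opposite directions.

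**The case against.** Several points on the other side stand.

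- **The eCRF rule is not exclusive.** Protocol 12.1 does not say that an eCRF is completed only for dosed men, and 9.5 points the other way. The SAP also expects some data on undosed men: its compliance listing records whether treatment was given, and its baseline tables use the randomized population. A reader might infer that an undosed man would certainly have no eCRF. The documents support only that the rules conflict and that his data may not be captured.
- **The supporting examples concern dosed men.** Protocol 5.2 mentions a vasovagal response after injection and partial administration during it. In both, drug was given. The attempt clause in Protocol 10.1 is the only text that contemplates an undosed man in the safety evaluation.
- **Worsening of underlying disease is not lost.** A reader might infer that post-injection worsening of, say, diabetes or hypertension drops out. Under Protocol 9.1, worsening of a condition present at baseline is itself an adverse event. Its onset is after dosing, so the date rule counts it. The gap is limited to adverse events that themselves began between screening and dosing.
- **Events in dosed men do not disappear.** SAP 9.4 lists all adverse events and gives an overall summary. Laboratory and ECG worsening also appears in change-from-baseline and shift tables.
- **The date rule can be read as sufficient rather than exclusive.** SAP section 6 does not say that only such events qualify, and the protocol's own definition of a treatment-emergent event has no worsening clause. The protocol and SAP therefore do not contradict each other on that definition. But the date is the only operational test given, and a programmer will apply it.

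None of this removes the mismatch between Protocol 10.1 and SAP section 5, or supplies a convention for worsening.

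**Conclusion.** The SAP safety population is narrower than the set in which the protocol says safety will be evaluated, and partial injections are left undefined. Protocol 12.1 and 9.5 need reconciling before one can be sure that an attempted-but-undosed man's data exist. The treatment-emergent rule needs a worsening clause and a finer time reference than the calendar date.

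For one attempted-but-undosed man with an event, the difference is about 7 to 9 percentage points in an 11-man arm and 6 to 8 points in the placebo arm, assuming planned arm sizes and zero to two other men with events. How many men would be affected is unknown, and it may be none.

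A reader might infer that these rules make the treatment look safer. The documents do not support a fixed direction. Omitting an attempted-but-undosed man with an event lowers his arm's incidence, and omitting a worsened event does the same, but counting dosing-day events that precede injection raises it. The effect on the comparison between arms depends on which arm the men are in. This is a definitional fault worth correcting before unblinding, and not evidence of a biased safety result.

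**What to change.** 1. **SAP section 5.** Align the safety population with Protocol 10.1: all randomized men in whom injection was attempted, started or partly given.
2. **Protocol 12.1.** Reconcile it with 9.5 by completing an eCRF for every randomized man.
3. **SAP section 6.** Define a treatment-emergent event as an adverse event with onset at or after the start of the injection procedure, including needle placement, or one present before it that increases in grade afterwards. Instruct sites to enter worsening as a new adverse event record dated at the change, and record the start time of the procedure. Starting the clock at the procedure matters, because a cut-off at completed injection would still miss a reaction at needle placement.

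The cost is wording in both documents, one CRF completion instruction and one recorded time. It needs no extra participants or visits. Reported incidence may change slightly in either direction.

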## 6. Definition

- **Age:** The age will be calculated as the exact number of days between the date of birth and date of informed consent converted to years (i.e. difference in days/365.25). Age is the integer part of this value.
- **Baseline:** The time point at which randomization is performed will be the baseline time point. The last instance of data collected before administration of treatment will be considered as the baseline information for the respective parameter. If a patient has repeated assessments prior to the start of double-blind study drug, then the results from the final assessment made prior to the start of double-blind study drug will be used as baseline.
- **Body Mass Index (BMI):** BMI is obtained by dividing the weight (kg) by the square of height (m) i.e. weight (kg)/ height (m).
- **Change between baseline and post dose visits** for the parameters will be considered as the difference between the post baseline value and the baseline value (post baseline value – baseline value). This will be applicable to laboratory data and safety parameters.
- **Prior/ Concomitant Medication/Therapy:** All medications/therapies with end date prior to the date of treatment will be considered as prior medications. Concomitant medication will be defined as any medication taken between the day of dosing with study drug and the end of the 6 month study follow-up period (or final visit). Any medications started after the final visit will not be considered concomitant medications.
- **Treatment Emergent Adverse Events (TEAEs):** A treatment emergent adverse event (TEAE) will be considered as an event that is temporally associated with the use of the study drug, whether or not considered related to the study drug. All adverse events with start date on or after the date of treatment will be considered as TEAEs.

**ION04ED**

**Serious Adverse Events:** Serious adverse events are defined as the adverse events which are medically significant events (e.g., intensive treatment in ER or at home for allergic bronchospasm), life threatening, requiring hospitalization or resulting in death, a disability, or a congenital abnormality.

## 7. Data Handling

Analysis using Last Observation Carried Forward (LOCF) will be used for handling missing data. Further, with regard to missing data, the assumption of missing at random will be assessed by looking for patterns over time, and by comparing those with missing values to all other subjects with regard to baseline characteristics. Chi-square or Exact tests will be used to compare incidence rates among the treatment cohorts with respect to the below baseline characteristics

- Demographics (date of birth, age, race, weight, height, and body mass index [BMI])
- Assessment of physical examination
- Abnormalities in ECG parameters
- Abnormalities in vital sign parameters
- Efficacy endpoints
- Safety endpoints
- Prior and concomitant medication

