7.6 Visit 6 (Study Week 12)

The following tests and evaluations will be performed:

- Adverse events and concomitant medications since last study visit;
- Physical examination including examination of penis;
- Vital signs (BP, heart rate);
- Electrocardiogram;
- Obtain plasma for the following laboratory determinations:
- Hematology: Complete Blood Count (CBC) with differential, platelet count,
- Chemistry: Blood Urea Nitrogen (BUN), creatinine, electrolytes (Na^+ , K^+ , Mg^{++} , Ca^{++} , CO_2 , Cl), albumin, alkaline phosphatase, LDH, GGT, ALT, AST, total bilirubin, total protein, glucose;
- Urine analysis: microscopic RBC and WBC, protein, glucose, nitrites and specific gravity;
- Plasma specimens will be collected to assay for the presence of *hSlo* DNA by PCR. These will be kept frozen at -20°C or less at the site for eventual assay by Sponsor.
- Participant completes the IIEF and SEP;
- Schedule next study visit.

7.7 Visit 7 (Study Week 24) or Exit Visit:

The following tests and evaluations will be performed:

- Adverse events and concomitant medications since last study visit;
- Physical examination including examination of penis;
- Vital signs (BP, heart rate, oral temperature, weight);
- Electrocardiogram;
- Obtain plasma for the following laboratory determinations:
- Hematology: Complete Blood Count (CBC) with differential, platelet count, Partial Thromboplastin (PTT), Prothrombin time (PT), sedimentation rate, C-reactive protein;
- Chemistry: Blood Urea Nitrogen (BUN), creatinine, electrolytes (Na^+ , K^+ , Mg^{++} , Ca^{++} , CO_2 , Cl), albumin, alkaline phosphatase, ALT, AST, LDH, GGT, total bilirubin, total protein, glucose;
- Endocrine: total testosterone, random cortisol, TSH, T4;
- Urine analysis: microscopic RBC and WBC, protein, glucose, nitrites and specific gravity;
- Plasma specimens will be collected to assay for the presence of *hSlo* DNA by PCR. These will be kept frozen at -20°C or less at the site for eventual assay by Sponsor.

- Participant completes the IIEF and SEP.

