8.0 Participant Withdrawal

While participants are encouraged to complete all study evaluations, they may withdraw from the study at any time and for any reason irrespective of the reason, or at the Investigator's decision. Participants who have been withdrawn from the study cannot be re-included in the study. Their inclusion and treatment number must not be re-used.

Participation is voluntary, and refusal to participate will involve no penalty, or loss of benefits to which the participant is otherwise entitled. The participant will be encouraged to maintain contact with the investigator and report any serious adverse events experienced for the 6 months study period. Follow-up following the study period is described in Section 7.9.

An **evaluable** participant will be any participant who receives at least one dose of test material and has at least one post dose assessment.

Screen failures will include any participant who consented and entered into the screening process appropriately, but subsequently did not meet the entry criteria and was not administered study drug. Participants who fail screening will not be followed for safety or activity of study drug, and no other study procedures will be performed.

Those participants who do not complete the study for any reason will be considered a premature termination. (eg. Adverse Event and/or lack of therapeutic effect and/or participants desire to discontinue study procedures/testing but allows for safety follow-up). The procedures for the Visit 7 should be completed when a participant discontinues the study.

- **Adverse Events:** Subjects with adverse events, severe enough to necessitate discontinuation of study drug administration as judged by the investigator. The treating physician should take appropriate clinical action. The condition should be treated according to routines of the clinic. The participant should be followed up regarding the safety measurements stated in the protocol.
- **Consent Withdrawn:** participant decided to withdraw his consent to participate in the study for any reason. In this event the participant refuses to participate in any additional evaluations and is withdrawing their consent for the site to utilize their data going forward. In this event the participant's data post the consent withdrawn will not be utilized in the clinical trial summary in accordance with enactment of 1996 (HIPAA) and subsequent Privacy Rule, required as of April 14, 2003.

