- **Lost to Follow-up:** participant failed to return for required visits and cannot be contacted. Reasonable effort should be made by the investigator to contact any

participant who fails to return to the clinic for a scheduled visit in order to complete assessments and retrieve any outstanding data or supplies of study medication. All such efforts should be documented in the source notes. Up to three participants “lost to Follow-up” can be replaced in each dosage cohort for participants that received gene transfer but failed to complete the Visit 4 (week 4) evaluations.

- **Sponsor/Investigator Decision:** A participant may be withdrawn at any time at the discretion of the Sponsor/investigator.
- **Lack of Therapeutic Effect:** A participant may choose to withdraw at any time if they feel that they want to pursue alternative treatment for their ED based on their perceived lack of therapeutic effect.

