## 9. Statistical Methods

This section describes the various statistical analyses that are planned to be performed for this study. The primary analysis which includes efficacy analysis will be performed on the mod-ITT population and supportive analysis on the PP and ITT populations. The safety endpoints will be evaluated on the safety population.

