### ION04ED

If a patient has repeated assessments prior to the start of double-blind study drug, then the results from the final assessment made prior to the start of double-blind study drug will be used as baseline. If end-of-study assessments are repeated or unscheduled, the last post-baseline assessment will be used as the end-of-study assessment for generating summary statistics. However, all post-baseline assessments will be presented in the data listings.

Dose response comparisons will be made between 8000 mcg vs. 16000 mcg vs. placebo as well as comparisons between total active population (8000 mcg and 16000) vs. placebo. Onset and duration of effect will also be analyzed and a dose response evaluated. Onset and duration of action will also be analyzed.

All tests of significance with regard to efficacy will be one-tailed, and performed at an overall alpha level of .05. All estimates of differences will be presented with 95% confidence limits.

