#### **Erectile Function (EF) domain of the International Index of Erectile Function (IIEF)**

The erectile function domain, questions 1-5, and 15 of the IIEF has been validated to assess erectile changes only. The IIEF EF domain has a 30-point total score, where higher scores reflect better erectile function. The EF domain of the IIEF will be completed at Visit 1 (screening) and V2-V7 (week 0-24).

The total score for a subject for the EF domain will be computed as the sum of the six questions. Descriptive statistics of the domain score will be presented with respect to the subjects receiving *hMaxi-K* (16,000 µg) and placebo at all visits. The change in scores from baseline at each visit will be evaluated using one-sided paired t-test at 5% significance level to assess improvement in scores post treatment when compared to baseline for the two treatment groups separately. Further, a one-sided two sample t-test will be applied to compare the changes from baseline in scores between the two treatment groups. The scores for the other 4 domains on the IIEF will also be computed and analyzed as secondary analyses.

Repeated measures ANOVA will be performed to assess the effect of visit on the total score for each treatment groups. Further a two-sample t test, will be performed to study the effect of treatment groups and time points on the domain scores.

The above analysis will be repeated for comparison between the two treatment cohorts and between *hMaxi-K* 8000µg and placebo treatment groups.

Analysis will be performed including all subjects and the final 15 subjects separately.

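### The visible SAP text handles missing data by LOCF alone and, for EF, omits the protocol's between-arm longitudinal model

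*SAP*

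**What the plan says.** **Missing data.** SAP section 7: "Analysis using Last Observation Carried Forward (LOCF) will be used for handling missing data". The same section plans to look at whether data are missing at random, but nothing follows from the answer. SAP section 9 adds "supportive analysis on the PP and ITT populations", which changes who is analysed and not how gaps are filled. The protocol does not mention LOCF.

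**EF analysis.** The protocol (Synopsis, Statistical Analysis; section 10.3.2) plans by-visit comparisons and also a mixed effects or marginal model across the treatment groups over time. SAP 9.3 has four pieces for EF:
- paired t-tests within each group;
- between groups, "a one-sided two sample t-test will be applied to compare the changes from baseline in scores between the two treatment groups";
- a repeated-measures ANOVA for visit, run for each group;
- a further two-sample t-test meant to cover both treatment and time.

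No between-arm longitudinal model and no baseline covariate appear. For SEP, SAP 9.3 does keep a between-arm repeated-measures logistic regression and an ANCOVA.

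**Late data.** SAP section 9: "Onset and duration of effect will also be analyzed and a dose response evaluated". Protocol 8.0: "A participant may choose to withdraw at any time if they feel that they want to pursue alternative treatment for their ED", on the ground of perceived lack of effect. Also in 8.0: "The procedures for the Visit 7 should be completed when a participant discontinues the study". Protocol 7.7 gives both occasions one label: "Visit 7 (Study Week 24) or Exit Visit". If end-of-study assessments are repeated or unscheduled, SAP section 9 says "the last post-baseline assessment will be used as the end-of-study assessment for generating summary statistics". That rule does not place an early exit score at the week it was taken.

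**The concern.** LOCF assumes that a man's score stays where it was when he left. Whether the score stays there is the question a duration analysis asks. LOCF is also not unbiased when data are missing at random, which is the assumption the SAP proposes to examine. The IIEF asks about the past month (Protocol Appendix D), so a Week 1 score carried forward would describe mostly time before dosing.

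The protocol's longitudinal model would have used every observed visit without imputation. Its SAP replacement does not do that job. Read as a t-test at each visit, the treatment-and-time sentence repeats the one before it. Read as estimating both effects together, it asks for something a two-sample t-test cannot give.

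At stake is how far a late-visit EF difference can be trusted as evidence of a lasting effect.

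**Working it through.** **1. The plan's own sample size.** Inputs (SAP section 8): means 10.0 and 6.6 (difference 3.4), SD 2.5, alpha 0.05/3 = 0.0167, power 80%, ratio 1.111. With the two-sided normal approximation, n = (2.393 + 0.842)² × 2.5² × (1 + 1/1.111) / 3.4² = 10.75, so 11. The placebo arm is 11 × 1.111 = 12.2, so 13. Total 35; 35/0.9 = 38.9, against the stated figure of about 40. The plan's figures reproduce.

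**2. Precision of one dose-placebo contrast.** SE = 2.5 × √(1/11 + 1/13) = 1.024. SAP section 9 makes efficacy tests one-tailed. At one-sided 0.0167 with 22 df, noncentral-t power is 84.6% with complete data.

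**3. LOCF bias when dropout follows a seen score.** These inputs are assumptions, because the documents do not give them:
- 10.0 and 6.6 are mean changes, and 2.5 is the SD of change;
- the correlation r between Week 4 and Week 24 changes is 0.4 to 0.8;
- a man leaves after Week 4 if his change is below 4.3.

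The standardised cutoffs are (4.3 - 10.0)/2.5 = -2.28 and (4.3 - 6.6)/2.5 = -0.92. Dropout is therefore 1.13% on active and 17.88% on placebo. That is (11 × 1.13 + 13 × 17.88)/24 = 10.2% of one contrast and (22 × 1.13 + 13 × 17.88)/35 = 7.4% of all 35 men.

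If both arms fall by d points between Week 4 and Week 24, the bias in active minus placebo is

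(1 - r) × 2.5 × (0.2613 - 0.0297) - d × (0.1788 - 0.0113),

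where 0.2613 and 0.0297 are the normal densities at the two cutoffs.

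| r | flat (d = 0) | fall of 4 | bias is zero at d = |
|---|---|---|---|
| 0.4 | +0.35 | -0.32 | 2.07 |
| 0.6 | +0.23 | -0.44 | 1.38 |
| 0.8 | +0.12 | -0.55 | 0.69 |

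Simulated power with LOCF is 85-87% (flat) or 79-81% (falling), against 84.6%. If dropout is equal in the arms, unrelated to outcome, and the arms move in parallel, the bias is zero.

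**4. A different time course.** Assume the effect builds in equal steps over the five post-dose visits. Men last seen at Week 1 then contribute one fifth of their final change, so an arm's LOCF mean is its true mean × (1 - 0.8p), with p the dropout.
- 5% active, 15% placebo: 10 × 0.96 - 6.6 × 0.88 = 3.79.
- 15% active, 5% placebo: 10 × 0.88 - 6.6 × 0.96 = 2.46.
- 10% in both: 3.4 × 0.92 = 3.13.

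If they are last seen at Week 12, the factor is (1 - 0.2p) and the first two become 3.50 and 3.17. The truth is 3.4 throughout.

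**5. Would a likelihood analysis do better?** It is unbiased in step 3, because dropout there depends on an observed score. Now let a man leave if his unseen Week 24 change is below the cutoff (4.3, or 0.3 when falling). LOCF bias becomes -(1 - r) × 2.5 × 0.2316 - d × 0.1675. That is -0.12 to -0.35 when flat and -0.79 to -1.02 when falling. A regression of Week 24 on Week 4 among completers with a pooled slope, simulated with 2,000,000 per arm, gives about -0.30 to -0.63 in both cases. It is worse than LOCF when flat and better when falling.

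**6. Baseline covariate.** Let ρ be the baseline-to-follow-up correlation and k the ratio of follow-up SD to baseline SD. Relative to change scores, the variance ratio is k²(1 - ρ²)/(1 + k² - 2ρk) × 1.05 (small-sample penalty), with 21 df.
- k = 1, ρ = 0.5: 0.75 × 1.05 = 0.79, power 92.0%.
- k = 2, ρ = 0.5: 1.00 × 1.05 = 1.05, power 82.5%.

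Over ρ = 0.3 to 0.7 and k = 1 to 2, power runs from 82.5% to 95%. Unequal SDs are plausible because the entry window in Protocol 4.1 restricts baseline EF but not follow-up.

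**7. SEP within-arm chi-square (minor).** SAP 9.3 compares post-dose with baseline answers of the same men. The diary is per attempt (Protocol Appendix C), SAP 9.2 tabulates subjects, and SAP 9.3 scores each man's percentage of positive answers. With m attempts per man per period, within-period correlation w and between-period correlation b, the true variance over the assumed variance is 1 + (m - 1)w - mb. One answer per man gives 1 - b, so the test is too conservative. With m = 4, w = 0.6, b = 0.3 it is 1.6, so a nominal 5% test rejects 2 × [1 - Φ(1.96/√1.6)] = 12.1%. With w = 0.5, b = 0.4 it is 0.9, and 3.9%. The error can go either way, on correlations the documents do not give.

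**The case against.** The size rests on an assumed dropout rule that puts nearly all losses on placebo, and the documents give no split by arm. The signs change with the assumptions. This stands, so no direction can be claimed. A reader might infer that LOCF flatters the active arms, and the documents do not support that.

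The SAP's 10% attrition covers all three arms, while the illustrated rule gives 7.4% of 35 men. This also stands; the rule is an illustration and is not calibrated to the SAP.

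A likelihood model can be worse than LOCF (step 5). This stands, and it is why a sensitivity analysis is needed as well as a new main model.

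The treatment-and-time sentence may be a misnamed test, since the SEP logistic regression sentence is worded much like it. That is possible, but the text as it stands still specifies no between-arm longitudinal model.

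Four stronger readings are tempting:
- *A breach of protocol.* Protocol 10.3 says the methods will be updated and the final SAP issued before the code is broken.
- *No second method anywhere.* The list of tables in SAP section 10 cannot be read in this copy, and the output shells are separate. An observed-case table can be neither confirmed nor excluded.
- *A separate Week 24 harm from the shared exit-visit label.* Under the SAP, LOCF carries the exit score to Week 24 whatever its label. The label matters only once a model uses the actual week.
- *A sure power gain from adjusting for baseline.* The protocol's model names no covariate either, and step 6 includes a small loss.

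**Conclusion.** The point holds, at moderate weight. The visible SAP text offers one missing-data method, and for EF it replaces a between-arm longitudinal model with analyses that do not do its work. On the step 3 assumptions the Week 24 bias lies between -0.55 and +0.35, up to about half a standard error, with a sign that cannot be fixed in advance. Harsher assumptions reach about -0.94 (step 4: 2.46 against 3.4) and -1.02 (step 5). Week 24 is used here for illustration, since neither document names a primary visit. The consequence is for how much a durability claim can bear; it does not undermine the trial as a whole. The SEP chi-square is a minor point: it is a within-arm test, and the planned between-arm SEP analyses are not at fault.

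**What to change.** **SAP 9.3, EF.** Replace the treatment-and-time t-test with one between-arm mixed model for repeated measures on EF change. Terms: treatment, visit, treatment-by-visit and baseline EF; Kenward-Roger degrees of freedom; a prespecified simpler covariance if the unstructured one fails. Name the visit for the main contrast. In that model, analyse early exit scores at the week they were taken, using stated analysis windows. Keep the by-visit t-tests as supportive.

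**SAP section 7.** Make LOCF a sensitivity analysis and add one missing-not-at-random analysis, for example a delta-adjusted tipping point.

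**SAP 9.3, SEP.** Drop the within-arm chi-square, or replace it with a paired comparison of each man's percentage of positive answers, reported descriptively. Rely on the planned between-arm analyses.

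**Cost.** SAP wording and a few lines of SAS on data already collected, before the treatment code is broken. There are three downsides. The unstructured model may not converge with 35 men. About 2 points of power are lost if baseline explains little (82.5% against 84.6%). The mixed model is itself biased if dropout depends on unseen scores.
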